COVER LETTER

Protocol Title: Phase II study of umbralisib plus ublituximab (U2) after CLL progression on targeted therapy

IRB Protocol #: 19-06020316

IND#: 144076

NCT#: NCT04149821

Version Date: May 24, 2021

Sponsor: Weill Cornell Medicine

Sponsor Investigator: [name].

Principal Investigator: [name].
[name]
[contact]
[contact]
[contact]

Participating Sites: Weill Cornell Medicine

This trial is supported by TG Therapeutics, Inc. (Tracking Number: U2-NTG-004)

Phase II study of umbralisib plus ublituximab (U2) after CLL progression on targeted therapy

IRB Protocol #: 19-06020316

IND#: 144076

Version Date: May 24, 2021

Sponsor: Weill Cornell Medicine

Sponsor Investigator: [name].

Principal Investigator:

[name].
[name]
[contact]
[contact]
[contact]

Co-Investigators:

[name] M.D.
[name] M.D.
[name] M.D.
[name] M.D.
[name] M.D. Ph.D
[name] M.D.
[name] M.D.
[name] M.D.
[name] M.D.
[name] M.D.
[name] M.D. Ph.D.

Statistician:

[name] Dr.Ph, M.S.

Participating Sites: Weill Cornell Medicine

This trial is supported by TG Therapeutics, Inc. (Tracking Number: U2-NTG-004)

Confidentiality Statement

This document is confidential and is to be distributed for review only to investigators, potential investigators, consultants, study staff, and applicable independent ethics committees or institutional review boards. The contents of this document shall not be disclosed to others without written authorization from WCM

Protocol Summary

Title: Phase II Study of umbralisib plus ublituximab (U2) after CLL progression on targeted therapy	
Study Drugs:	Umbralisib Ublituximab
Indication:	BTK or BCL-2 inhibitor Resistant CLL
Study Phase:	Phase II
Subjects to be enrolled:	24 subjects Cohort A Post BTKi Therapy: 12 Subjects Cohort B Post BCL-2 Therapy: 12 Subjects

Background and Rationale:

Novel agents have permanently altered therapeutic strategies in patients with chronic lymphocytic lymphoma (CLL). In relapsed settings, Bruton's tyrosine kinase (BTK), B cell lymphoma-2 (Bcl-2) and Phosphatidylinositol 3 kinase delta (PI3K δ) inhibitors have proven efficacy and garnered FDA approval in multiple therapeutic settings. Each drug demonstrates unique toxicities, efficacy, drug-drug interactions and monitoring schedules, making patient and disease specific characteristics important to consider when prescribing a particular therapy. For CLL, ibrutinib, a BTK inhibitor (BTKi), has become a standard of care for frontline therapy and is commonly the first line novel agent in patients with relapsed or refractory disease, owing to its ease of administration, safety profile, and durable efficacy[1-3]. Venetoclax, a Bcl-2 inhibitor, has also been shown to be safe and effective in salvaging BTKi resistant disease and is now approved as a frontline therapy in combination with obinutuzumab and for patients with relapsed CLL after 1 prior line of treatment in combination with rituximab [4-6]. Its use is complicated by a potential for life threatening tumor lysis which requires an intensive monitoring program during initiation and dose escalation, which can be burdensome to patients and physician practices, and may limit its widespread use outside of academic centers. Lastly, the use of PI3K δ inhibitors such as idelalisib or duvelisib, have been relegated to third or fourth line treatment options largely due to historically inferior efficacy and toxicity secondary to increased infectious risks and autoimmune complications such as colitis, pneumonitis and hepatitis [7, 8].

Despite the increasing numbers of therapeutic options, the optimal sequencing of therapies remains unknown with only limited retrospective data available estimating therapeutic benefit of each class of drug after progression on a BTKi.

Umbralisib, a PI3K δ inhibitor, has proven safe and effective in relapsed disease when combined with ibrutinib and or ublituximab [9, 10]. Umbralisib is built on a different chemical backbone than previous PI3K δ inhibitors such as idelalisib and duvelisib, and to date has demonstrated a significantly improved safety profile making it an attractive option as a salvage regimen in patients with BTK or BCL2 resistant disease.

Methodology:

We propose a single center Phase II study to evaluate the efficacy and safety of umbralisib and ublituximab (U2) as salvage in patients with CLL who have progressed either on a BTK inhibitor or BCL-2 inhibitor. The study will enroll in two parallel cohorts and subjects will be assigned based on which class of novel agent containing regimen was used prior. **Cohort A** will consist of patients who progress after BTKi containing regimens and **Cohort B** will consist of patients who progress after a BCL-2 containing regimens. Subjects who progress on a regimen containing both a BTKi and a BCL-2 inhibitor, will be enrolled in cohort B. Each cohort will be evaluated independently of each other.

Objectives:

Primary Objective: The primary objective of this study will be to evaluate the overall response rate (ORR) of umbralisib in combination with ublituximab in patients with CLL who have progressed on a BTK or BCL-2 inhibitor.

Secondary Objectives: Secondary objectives will be to evaluate complete remission rate, duration of response and safety.

Exploratory Objectives: Progression free survival (PFS) and overall survival (OS) will be assessed as exploratory objectives. We will also be collecting samples for future use in research as yet undetermined subject to review and approval by TG Therapeutics, Inc. Potential correlative studies may evaluate molecular predictors of response or resistance, changes in immune profile, and clonal evolution patterns in patients exposed to U2.

Drug Administration and Study Schedule:

Subjects that meet eligibility criteria will be enrolled and initiate therapy with umbralisib monotherapy for a one cycle lead in Cycle -1. During this lead in cycle of 28 days subjects will initiate umbralisib monotherapy at 800mg orally daily. Starting at C1D1 subjects will initiate combination therapy with U2, on 28 day cycles. During combination therapy, starting cycle 1 subjects will be treated with umbralisib 800mg orally daily and continue daily dosing through all subsequent cycles. Ublituximab will be co-administered on days 1 and 2 (split over days 1 and 2), 8, 15 of Cycle 1 then on D1 for subsequent cycles 2-6. After cycle 6, combination therapy will be completed and subjects will continue with monotherapy umbralisib daily. Subjects will be eligible for response assessment if they complete two cycles of therapy or are noted to have documented clinical progression of disease prior to first study mandated radiographic assessments. Radiographic evaluation for response will occur prior to C3, then occur prior to C7D1 and then every 6 months for up 2 years. Subjects who remain on study after two years will be radiographically evaluated annually thereafter until complete remission or upon evidence of clinical progression. Subjects that have achieved a CR will be followed clinically with physical exam and labwork but will not be required to undergo routine scanning. Study visits will occur monthly on D1 for Cycles 1-7 then every 3 months thereafter as long as patient continues to have clinical benefit.

Subject Selection:

Inclusion Criteria:

A subject will be eligible for participation in the study if he/she meets the following criteria:

1. Subject must have confirmed diagnosis of CLL/SLL and a treatment indication based upon 2018 International Workshop on CLL (IWCLL) criteria.
2. Subject must have documented disease progression on a BTK and or BCL-2 containing regimen as the most recent prior line of therapy. Subjects who were treated with a regimen containing both classes of novel agents will be allowed to enroll and will be enrolled into Cohort B. Subjects who receive a temporizing non-experimental treatment such as monotherapy with an anti-CD20 monoclonal antibody or corticosteroids including high dose methylprednisolone for up to 2 cycles immediately after progression on a BTK or BCL-2 inhibitor will be considered for enrollment after discussion with the study sponsor.
3. Subject must be ≥ 18 years of age.
4. Subject must have an Eastern Cooperative Oncology Group performance status of ≤ 2 .
5. Subject must have adequate bone marrow function to meet the below thresholds.
 - a. Absolute neutrophil count of >750 cell/ μ L in absence of G-CSF for 7 days prior to screening.
 - b. Platelet count of $\geq 30,000$ cells/ μ L independent of transfusion for 21 days prior to enrollment
6. Subject must have adequate organ function and meet the thresholds below:
 - a. Total bilirubin ≤ 1.5 times the upper limit of normal (ULN). Subjects with bilirubin exceeding this limit due to Gilbert's disease are eligible.
 - b. Alanine aminotransferase (ALT) and aspartate aminotransferase (AST) $\leq 2.5 \times$ ULN if no liver involvement or $\leq 5 \times$ the ULN if known liver involvement.
 - c. Creatinine clearance >30 ml/min/1.73m 2 as calculated by the MDRD equation.
7. Ability to swallow and retain oral medication.
8. Female subjects who are not of child-bearing potential (see Appendix: CONTRACEPTION GUIDELINES AND PREGNANCY), and female subjects of child-bearing potential who have

a negative serum pregnancy test within 3 days prior to initial trial treatment. Male subjects of reproductive potential may not participate unless they agree to use medically acceptable contraception. Female subjects of child-bearing potential and all male partners, and male subjects must consent to use a medically acceptable method of contraception throughout the study period and for 4 months after the last dose of study drug.

9. Willingness and ability to comply with trial and follow-up procedures, and give written informed consent.

Exclusion Criteria:

A subject will be ineligible for the study if he/she meets any of the following criteria:

10. Subject has had prior exposure to a PI3K inhibitor at any point in treatment history.
11. Subject has discontinued the BTKi or BCL2 due to intolerance. Intolerance will be defined as discontinuing prior BTKi or BCL2 therapy for any reason without evidence of progression. Subjects who were re-challenged after discontinuation for therapeutic reasons will be allowed if the toxicity did not recur or was managed without indication for discontinuation. Subjects who progress on BTKi or BCL2 therapy who were on a reduced dose due to an AE/intolerance are eligible as long as progression has been documented on that reduced dose.
12. Subject has history of or clinical or radiographic evidence of, or has biopsy proven Richter's transformation or prolymphocytic leukemia.
13. Subject has undergone an allogeneic stem cell transplant.
14. Subject has received an autologous hematologic stem cell transplant within 6 months of study entry.
15. Malignancy within 3 years of study enrollment except for adequately treated basal, squamous cell carcinoma or non-melanomatous skin cancer, carcinoma in situ of the cervix, superficial bladder cancer not treated with intravesical chemotherapy or BCG within 6 months, localized prostate cancer and PSA <1.0 mg/dL on 2 consecutive measurements at least 3 months apart with the most recent one being within 4 weeks of study entry.
16. Subject is known to be positive for HIV.
17. Subject has history of hepatitis C infection, active infection with hepatitis B or active cytomegalovirus (CMV) as determined by positive PCR.
18. Previous exposure to BTK or Bcl-2 inhibitor therapy within 14 days of initiating study treatment on Cycle - 1 Day 1, or previous exposure to anti-cancer therapy including chemotherapy, radiotherapy, or investigational therapy, including other investigational targeted small molecule agents within 21 days of initiating study treatment on Cycle 1 Day 1.
19. Evidence of ongoing systemic bacterial, fungal or viral infection, except localized fungal infections of skin or nails.
20. History of anaphylaxis (excluding infusion related reactions) in association with previous anti-CD20 administration.
21. A known history or active autoimmune disease even if not requiring systemic immunosuppression. Subjects with known history of immune thrombocytopenic purpura or autoimmune hemolytic anemia secondary to CLL are allowed to enroll. Malabsorption syndromes
22. Irritable bowel syndrome with greater than 3 loose stools per day as a baseline.
23. Any severe and/or uncontrolled medical conditions or other conditions that could affect participation in the study such as:
 - a. Symptomatic, or history of documented congestive heart failure (New York Heart Association functional classification III-IV [see Appendix: NYHA Classifications])
 - b. Significant cardiovascular disease such as uncontrolled or symptomatic arrhythmias, CHF, or myocardial infarction within 6 months of enrollment.
 - c. Concomitant use of medication known to cause QT prolongation or torsades de pointes should be used with caution and at investigator discretion.

- d. Poorly controlled or clinically significant atherosclerotic vascular disease including cerebrovascular accident (CVA), transient ischemic attack (TIA), symptomatic peripheral arterial disease, angioplasty, cardiac or vascular stenting within 6 months of enrollment.

24. Females who are pregnant or lactating.

Statistical Analysis Plan:

Currently available retrospective evidence demonstrates an ORR of ~35-40% when idelalisib is used as first salvage after ibrutinib failure [11]. Given umralisib's unique molecular properties and combination therapy with ublituximab, we hypothesize a response rate of 55% using U2 as first salvage. Salvage rates with novel agents after venetoclax failure in subjects considered double refractory are unknown. We anticipate close to 90% of patients enrolled in cohort B will have double refractory disease and represent a high risk group. Given these limitations, we anticipate a response rate of 40% in this group based off the efficacy seen with idelalisib after ibrutinib failure.

Because this is a pilot study, no formal sample size/power calculation is required. Given the anticipated different patient populations in each cohort, no cross cohort comparisons will be performed. However, with 12 patients enrolled in cohort A, an exact binomial (Clopper-Pearson) 95% confidence interval for the overall response rate can be constructed to have a width of approximately 57.6% (25.0%, 82.5%). This calculation assumes that the overall response rate will approach 55% in cohort A.

Similarly, with 12 patients enrolled in cohort B, an exact binomial (Clopper-Pearson) 95% confidence interval for the overall response rate can be constructed to have a width of approximately 56.9% (14.1%, 70.9%). This calculation assumes that the overall response rate will approach 40% in cohort B.

Given this is a pilot study with low subject enrollment with lack of power, analysis of outcomes will remain descriptive. Assuming adequate follow-up time, Kaplan-Meier survival analysis will be used to assess, progression-free survival (PFS), and overall survival (OS), in the entire cohort. All p-values will be two-sided with statistical significance evaluated at the 0.05 alpha level. Ninety-five percent confidence intervals for 1) the overall response rate, 2) median PFS/OS-time, and 3) PFS/OS proportions, will be calculated to assess the precision of the obtained estimates. All analyses will be performed in SAS Version 9.4 (SAS Institute, Inc., Cary, NC) and Stata Version 15.0 (StataCorp, College Station, TX).

Table of Contents

1. STUDY OBJECTIVES.....	8
1.1. Primary Objectives	8
1.2. Secondary Objectives	8
1.3 Exploratory Objectives.....	8
2. BACKGROUND	8
2.1 Disease.....	8
2.2 Rationale.....	9
2.3 Investigational Agents - Umbralisib.....	10
2.3.1 Umbralisib	10
2.3.2 Umbralisib Non-Clinical Studies	10
2.3.3 Non-Clinical Pharmacokinetics.....	11
2.3.4 Non-Clinical Toxicity.....	11
2.3.5 Umbralisib Clinical Pharmacokinetics/Pharmacodynamics	12
2.3.6 Umbralisib Clinical Studies.....	12
2.4 Investigational Agents – Ublituximab.....	13
2.4.1 Ublituximab	13
2.4.2 Ublituximab Non-Clinical Studies	13
2.4.3 Ublituximab Non-Clinical Pharmacokinetics	14
2.4.4 Ublituximab Clinical Pharmacokinetics/Pharmacodynamics	14
2.4.5 Ublituximab Clinical Studies Safety/Efficacy	15
2.5 Risk/Benefit Assessment.....	16
3. SUBJECT SELECTION	17
3.1 Study Population	17
3.2 Inclusion Criteria.....	17
3.3 Exclusion Criteria.....	18
4. REGISTRATION PROCEDURES.....	20
4.1 Patient Registration.....	20
5. STUDY PROCEDURES	20
5.1 Schedule of Evaluations	20
5.1.1 Screening Visit	24
5.1.2 Treatment Phase	24
5.2. Treatment Administration	27
5.2.1 Ublituximab	28
5.2.2 Management of Infusion Related Reactions	29
5.2.3 Umbralisib	30
5.3 General Concomitant Medication and Supportive Care Guidelines	31
5.4 Duration of Therapy and Criteria for Removal from Study	31
5.4.1 Procedures for Subject Removal if Less Than PR at Completion of Combination Therapy.....	32
5.5 Duration of Follow Up	32

6. DOSING DELAYS/DOSE MODIFICATIONS	33
6.1 Ublituximab	33
6.2 Umbralisib	33
7. PHARMACEUTICAL INFORMATION.....	38
7.1 Investigational Agent – Ublituximab	38
7.2 Investigational Agent – Umbralisib	39
7.3 Availability	39
7.4 Investigational Agent Ordering	39
7.5 Investigational Agent Accountability	40

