5.1 Schedule of Evaluations

Table 1. Schedule of trial events

Schedule of Assessments				Year 1										
Study Procedure	Screening	C-1	C-1	Cycle 1				C2 D1	C3 D1	C4 D1	C5 D1	C6 D1	C7 D1	C10 D1
		D1	D15	Day 1	Day 2	Day 8	Day 15							
Informed Consent	X													
Inclusion/Exclusion	X													
ECOG	X	X	X	X				X	X	X	X	X	X	X
Demographics	X													
Medical History	X	X	X	X	X	X	X	X	X	X	X	X	X	X
Physical Exam	X	X	X	X	X			X	X	X	X	X	X	X
Vital Signs	X	X	X	X	X	X	X	X	X	X	X	X	X	X
Height	X													
Weight	X	X	X	X				X	X	X	X	X	X	X
EKG	X													
Bone Marrow Biopsy	X													
Bone Marrow Aspirate	X													
CBC with diff	X	X	X	X	X	X	X	X	X	X	X	X	X	X
Serum Chemistry (CMP) ^a	X	X	X	X	X	X	X	X	X	X	X	X	X	X
HIV Rapid Screen	X													
Hepatitis Antibody Screen ^b	X													
Cytomegalovirus (CMV) PCR	X										X			X
B-HCG ^c (FCBP only)	X													
Circulating DNA (research)		X		X				X						X
Clonal Evolution Analysis (research)		X		X				X						X
Ublituximab Infusion			X	X	X	X	X	X	X	X	X	X	X	
Umbralisib Dispensation		X	X	X				X	X	X	X	X	X	X
Adverse Event Monitoring ^d	At each timepoint AEs will be collected													
Radiologic Evaluation ^e	X							X						X

Schedule of Assessments	Year 2				Year 3+	EOT	Follow-up*
Study Procedure	C13 D1	C16 D1	C19 D1	C22 D1	C25 D1 then Every 3 months	30 days post last dose	Every 3 months
Informed Consent							
Inclusion/Exclusion							
ECOG	X	X	X	X	X	X	X
Demographics							
Medical History	X	X	X	X	X	X	X
Physical Exam	X	X	X	X	X	X	X
Vital Signs	X	X	X	X	X	X	X
Height							
Weight	X	X	X	X	X	X	X
EKG							
Bone Marrow Biopsy							
Bone Marrow Aspirate							
CBC with diff	X	X	X	X	X	X	X
Serum Chemistry (CMP) ^a	X	X	X	X	X	X	X
HIV Rapid Screen							
Hepatitis Antibody Screen ^b							
Cytomegalovirus (CMV) PCR	X	X	X	X	X		
B-HCG ^c (FCBP only)							
Circulating DNA (research)	X		X		X	X	
Clonal Evolution Analysis (research)	X		X		X	X	
Ublituximab Infusion							
Umbralisib Dispensation	X	X	X	X	X		
Adverse Event Monitoring ^d	At each timepoint AEs will be collected						
Radiologic Evaluation ^e	X		X				X (q12mo)

Footnotes:

- * Subjects who discontinue treatment due to toxicity, but have not progressed will continue in study follow-up. Visits should occur q3months after EOT visit or until subsequent non-study drug administration. Patients who discontinue treatment due to progression of disease will enter survival follow-up. Survival follow-up will be documented by phone call every 6 months up to 5 years.

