5.1.2.6 Cycle 2-6, Day 1 (+/- 2 days)

- ECOG
- Medical history
- Physical exam

- Vital Signs
- Weight
- CBC with differential
- CMP
- Research tubes (2 purple top tubes for banking) (Cycle 2 only)
- Ublituximab infusion (+/- 3 days)
- Umbralisib pill dispensation
- CT neck, chest, abdomen and pelvis with contrast (Prior to C2D1 only +/- 7 days)
- CMV testing by PCR
- Adverse event assessment

5.1.2.7 Cycle 7, Day 1 and Beyond, Study visits occur every 3 cycles with a Day 1 visit (+/- 5 days)

- ECOG
- Medical history
- Physical exam
- Vital Signs
- Weight
- CBC with differential
- CMP
- Research tubes (2 purple top tubes for banking) (Cycle 7, 13, 19, 25 only)
- Umbralisib pill dispensation
- CT neck, chest, abdomen and pelvis with contrast (Prior to C7D1, C13D1, C19D1, C25D1 only +/- 7 days)
- CT neck, chest, abdomen and pelvis C37D1, C49D1, C61D1 +/- 7 days for subjects on study beyond 2 years.
- CMV testing by PCR
- Adverse event assessment
- After Cycle 7D1 study visit and response assessments subjects must be evaluated for objective response by treating investigator. See Section 5.4.1 for further details in subject management.

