11.4.2 Evaluation of Response

All subjects included in the study will be assessed for response to treatment if they have completed at least one cycle of ublituximab and umbralisib combination therapy.

12. Adverse Event Reporting Requirements

Adverse event (AE) monitoring and reporting is a routine part of every clinical trial. The investigator will be required to provide appropriate information concerning any findings that suggest significant hazards, contraindications, side effects, or precautions pertinent to the safe use of the drug or device under investigation. Safety will be monitored by evaluation of adverse events reported by patients or observed by investigators or research staff, as well as by other investigations such as clinical laboratory tests, radiographic imaging, and physical exam.

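### The first response CT is set before C3 in the Summary but before C2D1 in Section 5.1.2.6, and two conflicting evaluability rules leave the ORR denominator unsettled

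*Combined protocol and SAP*

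**What the plan says.** **Scan time.** The Protocol Summary (Drug Administration and Study Schedule) states: "Radiographic evaluation for response will occur prior to C3, then occur prior to C7D1". Section 5.1.2.6, which covers Day 1 of Cycles 2 to 6, lists a single CT: "CT neck, chest, abdomen and pelvis with contrast (Prior to C2D1 only +/- 7 days". It lists none before C3. Section 5.1.2.7 continues with "Prior to C7D1, C13D1, C19D1, C25D1 only +/- 7 days", so the scan before C7D1 is common to both versions. In the copy reviewed, the radiology row of Table 1 seems to fit C2D1, but its columns are not reliably aligned and nothing here rests on it.

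**Who is assessed for response.** The Summary states: "Subjects will be eligible for response assessment if they complete two cycles of therapy or are noted to have documented clinical progression" before the first mandated scan. Section 11.4.2 instead assesses subjects "if they have completed at least one cycle of ublituximab and umbralisib combination therapy". It has no clause for early progression.

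**Where these feed in.** ORR is the primary endpoint (Section 1.1). Duration of response starts at the first objective response (Section 9.2), and PFS ends at the first sign of progression or at death (Section 9.3). Section 11.2.1 bases the ORR intervals on 12 enrolled patients per cohort.

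**The concern.** Two current parts of the protocol give different times for the only CT between baseline and C7D1, so a site cannot follow both. The time chosen determines when an early response or early radiographic progression can first be dated. It also determines when the Summary's early-progression clause stops applying, because that clause is tied to the first mandated scan.

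Separately, the two evaluability rules do not admit the same subjects. With 12 per cohort, one subject moved in or out of the denominator is visible in the primary result. If the rule is left open, the choice can be made after the outcomes are known. The subjects affected are those who leave early, who are less likely than others to be responders.

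**Working it through.** **1. The plan's own figures.** Section 11.2.1 gives 95% Clopper-Pearson intervals for n = 12 at assumed rates of 55% and 40%. The lower limit is the 0.025 quantile of Beta(x, n − x + 1) and the upper limit is the 0.975 quantile of Beta(x + 1, n − x), with x = np.

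- Cohort A: x = 12 × 0.55 = 6.6, giving 24.96% to 82.54%, width 57.58 (stated 25.0%, 82.5%, 57.6%).
- Cohort B: x = 12 × 0.40 = 4.8, giving 14.06% to 70.94%, width 56.88 (stated 14.1%, 70.9%, 56.9%).

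Both reproduce and are not disputed. They show that the planned denominator is all 12 enrolled patients.

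**2. Scan times.** Section 5.2 gives 28-day cycles and a one-cycle lead-in. Take Cycle -1 Day 1 as day 1.

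- C1D1 = 1 + 28 = day 29
- C2D1 = 29 + 28 = day 57, after 28 days of combination therapy
- C3D1 = 57 + 28 = day 85, after 56 days of combination therapy
- C7D1 = 85 + 4 × 28 = day 197

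The gap is 85 − 57 = 28 days. The stated window around C2D1 is days 50 to 64. If the same 7 days were allowed around C3 (an assumption), that window would be days 78 to 92. The two do not overlap.

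**3. Effect on dates.** A subject already in response at C2D1 is dated about 28 days later if the first scan is before C3. For a subject whose response first becomes detectable between C2D1 and C3, the shift goes the other way. The C3 schedule dates it at day 85 and the C2D1 schedule at day 197, a difference of 112 days if no other CT is done. A subject whose response appears only after C3 is unaffected.

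**4. Who is in the denominator.** This table applies each rule as written, at nominal scan days.

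| Treated subject | Summary rule, CT before C3 | Summary rule, CT before C2D1 | Section 11.4.2 |
|---|---|---|---|
| Clinical progression before finishing combination cycle 1 | In, by progression clause | In, by progression clause | Out |
| Finishes combination cycle 1, clinical progression in cycle 2 | In | In only if Cycle -1 counts | In |
| Finishes combination cycle 1, stops in cycle 2 for another reason | In only if Cycle -1 counts | In only if Cycle -1 counts | In |
| Stops during combination cycle 1 for another reason | Out | Out | Out |

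The rules disagree in the first row whatever the scan date. The scan date matters only in the second row, and there only if Cycle -1 is not counted.

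**5. Size of the denominator effect.** The documents give no rate of early leaving, so 0, 1 or 2 of 12 is assumed, all non-responders.

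| Responders | None dropped | One dropped | Two dropped |
|---|---|---|---|
| 5 | 5/12 = 41.7% | 5/11 = 45.5% | 5/10 = 50.0% |
| 6 | 6/12 = 50.0% | 6/11 = 54.5% | 6/10 = 60.0% |
| 7 | 7/12 = 58.3% | 7/11 = 63.6% | 7/10 = 70.0% |

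**The case against.** The strongest reply is that this is one stray phrase in the Summary and that little follows from it. Several parts of that reply stand.

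- **Pairing of scan and rule.** A reader might infer that each scan time belongs to one evaluability rule: C3 with two cycles, C2D1 with one combination cycle. The documents do not establish this. The Summary speaks of cycles of therapy, and Section 5.2 treats Cycle -1 as a treatment cycle. If it counts, two cycles end at C2D1 and the two thresholds coincide.
- **Primary endpoint.** A reader might infer that ORR itself has two competing assessment times. No section ties ORR to the first scan, or says whether it is best response or response at a fixed visit. Sections 5.2 and 5.4.1 call for a formal response evaluation at C7D1, which both schedules share. For subjects who reach it, ORR may change little.
- **Early leavers.** It would be too strong to say that they generally have no scan and drop out. The Summary keeps those with documented clinical progression before the first scan. Section 5.5 provides follow-up CT every 12 months or when clinically indicated for those who stop for other reasons.
- **Attribution.** The shift from 6/12 to 6/11 comes from the evaluability rule, not from the scan date. It is also small beside intervals about 57 points wide in a descriptive pilot.

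The reply does not remove the contradiction between the two scan times. Nor does it address the literal effect of Section 11.4.2, which excludes a treated subject who fails before completing combination cycle 1 although the planned intervals count all 12.

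**Conclusion.** The point holds as an internal inconsistency with two parts. First, the Summary and Section 5.1.2.6 place the first on-treatment CT 28 days apart, and the stated tolerance cannot reconcile them. Section 5.1.2.6 does not label its scan a response scan, but it is the only on-treatment CT before C7D1 in the visit lists. Second, the Summary and Section 11.4.2 define evaluability differently, and only the Summary retains subjects with early clinical progression.

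The consequences are limited mainly to early leavers and to the dating of response and progression. The 28-day shift in first response applies only to subjects already responding at C2D1; it is not a general shift in duration of response. For ORR, each dropped non-responder adds roughly 4 to 6 points in the range shown. This assumes one or two early leavers per cohort, none of them responders, and illustrates the denominator rule alone.

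**What to change.** - Reconcile the Summary, Table 1 and Section 5.1.2.6 to one time for the first response CT, stated identically in each. This review does not say which time is right.
- State whether Cycle -1 counts as a cycle of therapy for evaluability.
- Replace the two evaluability rules with one, worded the same in the Summary and in Section 11.4.2.
- Define the primary ORR in each cohort as responders divided by all treated subjects, with those who have no response assessment counted as non-responders. This agrees with the n = 12 in Section 11.2.1, provided every enrolled subject is treated. An ORR in evaluable subjects only can be reported as a sensitivity analysis.

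The cost is protocol wording; no scan is added. The reported ORR may be slightly lower, because early leavers remain in the denominator.
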